11.1.4 Response Criteria (Modified to define Minor Response and progressive disease category)

11.1.4.1 Evaluation of Target Lesions

Complete Response (CR): Disappearance of all target lesions. Any pathological lymph nodes (whether target or non-target) must have reduction in short axis to <10 mm.

Partial Response (PR): At least a 30% decrease in the sum of the diameters of target lesions, taking as reference the baseline sum diameters.

Minor Response (MR): 20%-29% decrease in the sum of the diameters of target lesions, taking as reference the baseline sum diameters.

Progressive Disease (PD): At least a 20% increase in the sum of the diameters of target lesions, taking as reference the smallest sum on study (this includes the baseline sum if that is the smallest on study). In addition to the relative increase of 20%, the sum must also demonstrate an absolute increase of at least 5 mm. (Note: unequivocal diagnosis of new non-bony tumor lesion is also considered progression. This is because it has been challenging to diagnose bony metastasis response/progression while patients are treated with such new class of drugs-i.e.: sometimes necrosis caused by

study drug is interpreted as ‘progression of lytic component).

Stable Disease (SD):

Neither sufficient shrinkage to qualify for MR or PR nor sufficient increase to qualify for PD, taking as reference the smallest sum diameters while on study.

11.1.4.2 Evaluation of Non-Target Lesions

Complete Response (CR): Disappearance of all non-target lesions and normalization of tumor marker level. All lymph nodes must be non-pathological in size (<10 mm short axis).

Note: If tumor markers are initially above the upper normal limit, they must normalize for a patient to be considered in complete clinical response.

Non-CR/Non-PD:

Persistence of one or more non-target lesion(s) and/or maintenance of tumor marker level above the normal limits.

Progressive Disease (PD):

Appearance of one or more new lesions and/or *unequivocal progression* of existing non-target lesions. *Unequivocal progression* should not normally trump target lesion status. It must be representative of overall disease status change, not a single lesion increase.

Although a clear progression of “non-target” lesions only is exceptional, the opinion of the treating physician should prevail in such circumstances, and the progression status should be confirmed at a later time by the review panel (or Principal Investigator).

11.1.4.3 Evaluation of Best Overall Response (Modified with confirmation of response required at 8 weeks rather than 4 weeks)

The best overall response is the best response recorded from the start of the treatment until disease progression/recurrence (taking as reference for progressive disease the smallest measurements recorded since the treatment started). The patient's best response assignment will depend on

the achievement of both measurement and confirmation criteria.

For Patients with Measurable Disease (i.e., Target Disease)

| Target Lesions | Non-Target Lesions | New Lesions | Overall Response | Best Overall Response when Confirmation is Required* | |
|--|-----------------------------|-------------|------------------|--|--|
| CR | CR | No | CR | >8 wks. Confirmation** | |
| CR | Non-CR/Non-PD | No | PR | ≥8 wks. Confirmation** | |
| CR | Not evaluated | No | PR | | |
| PR | Non-CR/Non-PD/not evaluated | No | PR | | |
| MR | Non-CR/Non-PD/not evaluated | No | MR | Documented at least once ≥8 wks. from baseline** | |
| SD | Non-CR/Non-PD/not evaluated | No | SD | | |
| PD | Any | Yes or No | PD | no prior SD, MR, PR or CR | |
| Any | PD*** | Yes or No | PD | | |
| Any | Any | Yes | PD | | |
| 
* See RECIST 1.1 manuscript for further details on what is evidence of a new lesion.
 
** Only for non-randomized trials with response as primary endpoint.
 
*** In exceptional circumstances, unequivocal progression in non-target lesions may be accepted as disease progression.
 | | | | | |
| 
Note: Patients with a global deterioration of health status requiring discontinuation of treatment without objective evidence of disease progression at that time should be reported as “symptomatic deterioration.” Every effort should be made to document the objective progression even after discontinuation of treatment.
 | | | | | |

For Patients with Non-Measurable Disease (i.e., Non-Target Disease)

| Non-Target Lesions | New Lesions | Overall Response |
|---|-------------|------------------|
| CR | No | CR |
| Non-CR/non-PD | No | Non-CR/non-PD* |
| Not all evaluated | No | not evaluated |
| Unequivocal PD | Yes or No | PD |
| Any | Yes | PD |
| * ‘Non-CR/non-PD’ is preferred over ‘stable disease’ for non-target disease since | | |

SD is increasingly used as an endpoint for assessment of efficacy in some trials so to assign this category when no lesions can be measured is not advised

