5. TREATMENT PLAN

5.1 Agent Administration

Patients will receive treatment depending on which treatment ARM patients are randomized to (see Figure 3. Treatment Schema). Please review entire Section 5.0 to review treatment of study agents as well as caution with concomitant medications.

[figure not shown]
Treatment will be administered on an outpatient, continuous basis. One cycle is defined as 28 days. Reported adverse events and potential risks are described in Section 7. Appropriate dose modifications are described in Section 6. No investigational or commercial agents or therapies may be administered with the intent to treat the patient's thyroid cancer.

The patient will be requested to maintain a medication diary documenting the dose of medication(s) and the date and time of each dose taken. The medication diary will be returned to clinic staff at the end of each cycle.

It is preferred that patients take all planned study agent on day 1 of each new cycle. Patients should be instructed to take scheduled doses on clinic visit days. Any dose delayed > 1 hour from scheduled time on day 1 of a new cycle due to pending safety assessments may still be taken so long as there is at least 12 hours between doses (per IBs). Alternatively, one dose of Trametinib and/or one or more doses of Dabrafenib may be missed on day 1 of a new cycle, if per local standard practice patients are

instructed by the treating physician to hold all dosing on clinic days until after the safety assessments have been completed. All missed doses and reasons are to be clearly documented in the source records and study case report forms.

Figure 3. Treatment Schema

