| 2-mL blood per time point for pharmacokinetics (Section 9.5) ⁿ | | Please see Section 9.5 for details of time points | | | | | |
| Paraffin tumor block (Section 9.4) | X | | | | | | |

| 10-mL blood for BRAF mutations in circulating plasma (Section 9.2) | | X | | | X ^r | X (Cycles 3 and 5 only) | X Only if PD |
|---|---|---|--|---------------------------|----------------|----------------------------|-----------------|
| Tumor Pharmacodynamics Tumor Biopsy (Section 9.1) | X | | | X ⁱ +/- 5 days | | | |
| Tumor Mutation Screening Tumor Biopsy (Section 9.3) | | | | | | | X Only if PD |

- a. If pre-study labs (CBC/diff, Chemistry) are drawn within 14 days of study entry, such labs do not have to be repeated on C1D1.
- b. All on-study visits can be performed within +/-3 days. For cycles 8 to 18, please follow same schedule as for even and odd cycles as Cycles 2, 4, 6 or Cycles 3, 5, 7 respectively. Please review all footnotes as some testing is not required as frequently after 1st 6 cycles.
- c. Off-therapy evaluations are to be conducted within 4 weeks after last dose of study drug (s). Labs do not need to be repeated if done within 2 weeks.
- d. Sodium, Potassium, Chloride, Bicarbonate, Creatinine, BUN, Glucose, Calcium, Phosphorus, Total protein, Albumin, Total bilirubin, SGOT (AST), SGPT (ALT), Alkaline phosphatase, lactate dehydrogenase (LDH).
- e. Pregnancy test (sensitivity of at least 50 mIU/mL) will be performed for all women of childbearing potential before beginning study drug (s).
- f. CT or MRI scans as determined by investigators to assess the response per RECIST v1.1 criteria. CTs or MRIs with IV contrast are encouraged but will be done per investigator's discretion. Scans can be done within 7 days prior to day 1 of cycles 3, 5, 7 and subsequent odd number of cycles. If CT abdomen is negative at baseline, they only need to be repeated if clinically indicated during the study period.
- g. PET scans are performed only as clinically indicated at pre-study, every 8 weeks and off study as determined by treating physicians.
- h. Echo or MUGA will be done pre-study and every 2 cycles for 6 cycles and then every 4 cycles x 18 months and then only if clinically indicated. Scans can be done within 7 days prior to day 1 of cycles 3, 5, 7 and subsequent odd number of cycles.
- i. This can be done any time +/- 5 days from C1D15. Not required during C2D15 time point.

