- j. Patients on both ARMs must have a dermatologic exam to monitor and manage side effects on the skin.
- k. All patients must have ophthalmologic exam at pre-therapy. Patients randomized to or crossed over to ARM B (combination treatment arm) should have these as clinically indicated. Patients are required to have a standard ophthalmic exam performed by an ophthalmologist at baseline, and as clinically warranted per protocol's guidance (Refer to Section 6.2.2 for visual changes stopping criteria). The exam will include indirect fundoscopic examination, visual acuity (corrected), visual field examination, tonometry, and direct fundoscopy, with special attention to retinal abnormality that are predisposing factors for RVO or CSR. For patients with clinical suspicion of RVO or CSR, fluorescein angiography and/or optical coherence tomography are highly recommended.
- l. Each cycle start is allowed a +/- 3 day window
- m. Patients taking Antiplatelets or Anticoagulants need to have a CBC every 2 weeks for the first 4 months.
- n. Patients that cross over from ARM A to ARM B are not eligible for the PK or PGx correlative studies.
- o. All patients will receive a follow up phone call a week after each clinic visit for the first 4 months of treatment. The team will confirm with the patient that they are taking the correct amount of study medication, and that they have enough study medication to last until their next clinic visit.
- p. After the completion of the 18th cycle, visits will be extended to every 8 weeks. All exams, tests, and scans listed for the odd cycle visits will be completed.
- q. Electrocardiogram (EKG) will be done pre-study and every 2 cycles for 6 cycles and then every 4 cycles x 18 months and then only if clinically indicated.
- r. After completion of the 18th cycle, visits will be extended to every 8 weeks. BRAF research labs will be drawn at every other visit (every 16 weeks) and at time of progression.

Baseline evaluations are to be conducted within 4 weeks prior to start of protocol therapy. Four weeks (28 days) is considered one cycle. A member of the study team will be making a follow up phone call to each patient a week after each clinic visit for the first 4 months of treatment. The team will confirm with the patient that they are taking the correct amount of study medication, and that they have enough study medication to last until their next clinic visit.

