11. MEASUREMENT OF EFFECT

11.1 Antitumor Effect – Solid Tumors

For the purposes of this study, patients should be evaluated for response every 8 weeks. Subsequent scan done at 8 weeks will serve as confirmatory scans following initial documentation of objective response.

Response and progression will be evaluated in this study using the new international criteria proposed by the revised Response Evaluation Criteria in Solid Tumors (RECIST) guideline (version 1.1) [Eur J Ca 45:228-247, 2009]. Changes in the largest diameter (unidimensional measurement) of the tumor lesions and the shortest diameter in the case of malignant lymph nodes are used in the RECIST criteria.

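### The confirmation minimum in section 11.1.4.3 equals or exceeds the 8-week scan spacing with no tolerance, so an on-schedule next scan can fail to confirm a response

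*Combined protocol and SAP*

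**What the plan says.** - **Scan spacing.** Section 11.1: "For the purposes of this study, patients should be evaluated for response every 8 weeks". Section 5.1: "One cycle is defined as 28 days". Scans are therefore two cycles, or 56 days, apart.
- **Scan window.** Section 10 (Study Calendar), footnote f: "Scans can be done within 7 days prior to day 1 of cycles 3, 5, 7 and subsequent odd number of cycles". Footnote l adds: "Each cycle start is allowed a +/- 3 day window". The sample calendar in Appendix D places the first on-study scan on days 50-56.
- **Intended confirmatory scan.** Section 11.1: "Subsequent scan done at 8 weeks will serve as confirmatory scans following initial documentation of objective response".
- **Written minimum.** The table in section 11.1.4.3 asks for ">8 wks. Confirmation" for a CR and "≥8 wks. Confirmation" for a PR. The cell beside MR, which appears to cover SD as well, reads "Documented at least once ≥8 wks. from baseline". No tolerance is given for any of the three.
- **Scope.** These cells carry a double-asterisk footnote that confines them to non-randomized trials with response as primary endpoint. The heading of 11.1.4.3 says that confirmation is required, at 8 weeks instead of 4, and the text beneath it makes best response depend on confirmation as well as measurement.

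**The concern.** A minimum interval set at the nominal spacing works only if scans never come early relative to one another, and footnote f expressly allows them to. Applied as written, the table can leave a sustained response unconfirmed because the second scan fell a few days earlier in its window than the first did. For CR the strict inequality rejects even an interval of exactly 8 weeks.

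What is at stake is how best response is classified, and therefore the confirmed PR+CR rate. Section 13.1.3 lists PR+CR among the factors to be weighed when the arms fall within 0.10 of each other. The plan does not say how an unconfirmed PR or CR is to be classed, so sites and analysts could handle the same scans differently.

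**Working it through.** **1. The plan's own figure.** The documents give no figure for confirmation failure. The nearest quantitative statement is the 90% probability of selecting the better regimen in section 13.1.3 (26 per arm, 15% versus 35%, margin 0.10, a 50/50 choice inside the margin). The exact binomial calculation gives:

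P(difference ≥ 0.10) + 0.5 × P(|difference| < 0.10) = 0.8138 + 0.5 × 0.1805 = 0.904.

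This reproduces 90%. The side statements also reproduce: 91.6% at 10% versus 30%, and 88.2% at 40% versus 60%. The design arithmetic is not in question.

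**2. Possible gaps between consecutive scans.** With 28-day cycles, day 1 of cycles 3, 5 and 7 falls on days 57, 113 and 169. If a scan is done e days early, then

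gap = 56 + e(first) − e(second).

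- e from 1 to 7 (the seven days shown in Appendix D): 50 to 62 days.
- e from 0 to 7 (counting day 1 itself): 49 to 63 days.
- e from 0 to 7, with each cycle start also moving by up to 3 days: shortest gap 56 − 7 − 3 − 3 = 43 days.

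Example: scans on day 110 (3 days before day 113) and day 162 (7 days before day 169) are both in window. The gap is 162 − 110 = 52 days, below the 56 required for a PR.

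**3. How often the next scan misses the minimum.** A PR fails if the gap is under 56 days; a CR fails if it is 56 days or less. The documents say nothing about how scan dates are distributed, so every row below is an assumption.

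| Assumed timing | PR misses | CR misses |
|---|---|---|
| Independent, uniform over 7 days | 21/49 = 42.9% | 28/49 = 57.1% |
| Independent, uniform over 8 days | 28/64 = 43.8% | 36/64 = 56.3% |
| 8 days, plus uniform ±3-day cycle starts | 45.5% | 54.5% |
| Independent, only 0 or 1 day early | 1/4 = 25% | 3/4 = 75% |
| Half of patients at a constant offset, half uniform over 8 days | 0.5 × 43.8% = 21.9% | 0.5 + 0.5 × 56.3% = 78.1% |
| Every patient at a constant offset (gap always 56) | 0% | 100% |

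**4. The MR/SD cell.** A first scan on days 50-56 is 49 to 55 days after day 1. If baseline means day 1, none of those scans reaches 56 days. If baseline means the pre-treatment scan, done k days before day 1, the interval is k + 49 to k + 55. With cycle starts on schedule it falls short only when k is 6 or less. Counting pairs for k = 1 to 6 gives 6 + 5 + 4 + 3 + 2 + 1 = 21 failing pairs. With k uniform over 1-28, 1-15 or 1-8 days, the failing share is 21/196 = 10.7%, 21/105 = 20.0% or 21/56 = 37.5%. These too are assumptions.

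**The case against.** The strongest reply is the double-asterisk footnote. This trial is randomized, so on a literal reading the three cells do not apply and no response can fail them. That cannot be dismissed. However, the heading of 11.1.4.3, the text under it and section 11.1 all impose confirmation in this study, and the heading shows that the interval was deliberately changed for it. The documents conflict, and the written minimum can still be applied.

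A second reply is that section 11.1 already supplies the working meaning: the next 8-week scan confirms. That is very probably the intent, but a table with a stated minimum is what a programmer would code.

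Third, the strict inequality for CR may be a typographical or extraction slip, since the PR cell reads at least 8 weeks. If so, the CR figures fall to the PR ones. The lack of tolerance remains.

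Fourth, the consequence may be small, and this largely stands. The primary endpoint in section 13.1.2 counts MR, PR or CR within 6 cycles and states no confirmation interval. MR needs only one documentation. A PR first seen at week 8 and missed at week 16 could still be confirmed at week 24. A PR first seen at the second scan has only the third (days 162-168) left within 6 cycles, but the plan does not say that confirmation must fall inside that period.

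**Conclusion.** The table's minimum conflicts with the scan window in section 10 and with section 11.1. Where it is applied, a compliant next scan can fail to confirm a PR, and a CR re-scanned at exactly 56 days always fails. Over the timing scenarios examined, the share missing the minimum at the next scan runs from 0% to about 46% for PR and from about 54% to 100% for CR. Independent uniform timing gives about 43-46% and 54-57%. The MR/SD cell has a similar but smaller problem, whose size depends on which date baseline means.

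Three stronger conclusions are tempting, and the documents do not support them:

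- **That 43% of PRs and 57% of CRs will fail.** Those figures need independent, uniform timing over 7 days, which the plan does not state.
- **That no MR at the first scan can ever qualify.** That needs baseline to mean day 1, whereas sections 11.1.2 to 11.1.4 use the word for pre-treatment measurements. An MR that persists to the next scan would qualify in any case.
- **That the trial loses primary-endpoint responders or selection power.** A margin of 0.10 × 26 = 2.6 patients does mean that three responders can decide the choice, but no loss of responders and no effect on the 90% is established.

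This is a wording conflict worth correcting, not an error in the design calculation.

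**What to change.** In the section 11.1.4.3 table:

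- Replace both confirmation cells (CR and PR) with: *confirmed at the next scheduled 8-weekly scan, within the protocol scan and visit windows*. Do not add a separate minimum in days or weeks. Even a 7-week (49-day) floor would reject compliant scans, since gaps can be as short as 43 days.
- Replace the MR/SD cell with: *documented at the first scheduled on-study scan (C3D1, within window) or later*.
- In the same edit, reconcile the double-asterisk footnote with the section heading and section 11.1, so that the protocol says once whether confirmation applies in this randomized trial. A sentence on how an unconfirmed PR or CR is classed would close the remaining gap.

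The cost is wording in one table and its footnote, with no extra scan. The downside is that a response may be confirmed up to about two weeks sooner than the nominal 8 weeks (56 − 43 = 13 days at the extreme of the windows).

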11.1.5 Duration of Response

Duration of overall response: The duration of overall response is measured from the time measurement criteria are met for CR or PR or MR (whichever is first recorded) until the first date that recurrent or progressive disease is objectively documented (taking as reference for progressive disease the smallest measurements recorded since the treatment started).

The duration of overall CR is measured from the time measurement criteria are first met for CR until the first date that progressive disease is objectively documented.

Duration of stable disease: Stable disease is measured from the start of the treatment until the criteria for progression are met, taking as reference the smallest measurements recorded since the treatment started, including the baseline measurements.

11.1.6 Progression-Free Survival

Progression-free survival (PFS) is defined as the duration of time from start of treatment to time of progression or death, whichever occurs first.

11.1.7 Response Review

Objective response review will be done by radiologists from each site where patient was treated.

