4.2 Registration Process

To register a subsite patient, the following documents should be completed by the research nurse or data manager and faxed or e-mailed to the Subsite Coordinator:

- Copy of all required laboratory and radiologic tests per the protocol calendar. Screening tests must be within the specified window.
- Signed patient consent form
- HIPAA authorization form
- Eligibility Criteria Checklist
- Registration Form
- Source documents verifying every inclusion & exclusion criteria
- Emails and other signed forms used as source documentation

The subsite research nurse or data manager at the participating site will then call or email the Subsite Coordinator to verify eligibility. To complete the registration process, the Coordinator will:

- assign a patient study number
- register the patient on the study
- randomize the patient to treatment ARM A or ARM B
- advise if patient will need Pharmacokinetic studies (as it is restricted to first 10 pts on each arm)
- fax or e-mail the patient study number and assigned treatment ARM to the participating site

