12.1 Data Reporting

12.1.1 Method

This study will be monitored by Ohio State University (Coordinating site) per their institutional guidelines for Multicenter Trials. Cumulative protocol- and patient-specific data will be submitted via Case Report Forms to The Ohio State University within 2 weeks of patient completion of each cycle/study time point.

12.1.2 Case Report Forms:

Case Report forms will be provided by OSU. In addition to case report forms, relevant reports on source documents will be requested to verify objective response. Actual CT or MRI images might be requested to verify objective response.

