13.1.3 Statistical Design

To both evaluate whether or not each of these experimental treatment regimens are sufficiently active in this patient population as well as to screen these regimens for the most promising regimen to be carried forward to the phase III setting, this study utilizes a flexible screening design developed by Sargent and Goldberg (*Statistics in Medicine*, 2001). Overall, we have developed this study to be able to determine that one regimen is decidedly worth pursuing further over another if the true differential in the overall response rates between arms is 0.20. Overall, we have developed this study to be able to determine that one regimen is decidedly worth pursuing further over another if the true overall response rates are 15% versus 35%. This study design has 90% power to identify the correct regimen as most promising and thus the regimen to bring forward into larger and confirmatory studies. Based on these assumptions and constraints, 26 evaluable patients will be accrued to each arm to evaluate the regimens under the parameters specified. If our underlying assumptions regarding the true response rates associate with each of these arms is a little lower (e.g. 10% vs. 30%), we will have additional power for these analyses (i.e. >90%). Even if our true response rates corresponding to the treatment regimens being evaluated here are higher (e.g. 40% vs. 60%), we will still have sufficient power (>88%) to determine that one arm is more promising than another if it truly is with this number of patients per arm and the same rule for observed differential described below. The main decision rule is based on differential, and the above assumptions show a flexibility and sufficient power for identifying the most promising regimen even if our hypotheses regarding response rates are slightly off.

As part of this design, we define one treatment arm to be more promising than another if the actual observed overall response rate for each of the arms differ by 10% or more, in which case the regimen with the higher overall response rate will be recommended for further testing. If these rates differ by less than 10%, factors

other than the overall response rate will be considered.

- If one treatment arm has an overall response rate that is at least 0.10 higher than the other, then it will be deemed the most promising and carried forward to the phase III setting.

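### No masking to arm is specified for the site radiologists who read the primary endpoint, although a lead of 3 responders in 26 selects the regimen; masking the measurement step would be cheap.

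*Combined protocol and SAP*

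**What the plan says.** Section 11.1.7 is one sentence: "Objective response review will be done by radiologists from each site where patient was treated". It does not say whether those radiologists know the treatment arm, and no other section does.

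The site itself knows the arm. Under section 4.2 the coordinator will "fax or e-mail the patient study number and assigned treatment ARM to the participating site". One arm takes one drug and the other takes two, no placebo is described, and only Arm A patients may cross over at progression (4.3).

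The primary endpoint (13.1.2) is minor, partial or complete response within 6 cycles. Minor response means a 20-29% fall in the sum of target-lesion diameters. Section 13.1.3 plans that "26 evaluable patients will be accrued to each arm" and calls one arm more promising if the "observed overall response rate for each of the arms differ by 10% or more". A smaller difference is referred to toxicity, PR+CR rate, progression-free survival and correlative markers. Substantially greater toxicity may override a clear lead.

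On verification, section 12.1.2 requires source reports to be requested to confirm response. It then adds: "Actual CT or MRI images might be requested to verify objective response". It gives no rule for choosing whose images are requested.

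**The concern.** The person who measures the lesions may know the arm, and the protocol states which arm it expects to do better (2.5). Such a reader could, without intending to, record a borderline case as a minor response in Arm B and as stable disease in Arm A.

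Four features make this trial sensitive to that.

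- The selection margin amounts to very few patients.
- The boundary between stable disease and response is set at 20% shrinkage with no minimum absolute change, whereas progression also requires 5 mm (11.1.4.1). A single 10 mm target lesion, which is measurable under 11.1.2, reaches minor response on a change of 0.20 × 10 = 2 mm.
- As the table in 11.1.4.3 reads, minor response needs to be recorded only once. A footnote limits the confirmation column to non-randomized trials, while 11.1 describes confirmatory scans. One read may therefore decide a responder.
- Among the factors that settle a close result, PR+CR and progression-free survival rest on the same reads.

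At stake is which regimen goes forward to Phase III.

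**Working it through.** **Inputs from section 13.1.3.** 26 patients per arm; margin d = 0.10; planning rates 15% vs 35%; half credit for a result inside the margin. The true rates in steps 3 and 4 and every bias size are assumptions, except that step 4 reuses the planning rates with the arms reversed.

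**Step 1: the margin in patients.** 0.10 × 26 = 2.6. A lead of 2 is 2/26 = 7.7%, inside the margin. A lead of 3 is 3/26 = 11.5%, outside it. The smallest deciding lead is 3 responders.

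**Step 2: reproduce the plan's power.** Let X_A ~ Bin(26, p_A) and X_B ~ Bin(26, p_B), independent. Sum the products of binomial probabilities over all pairs of counts:

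P(correct) = P(better arm leads by ≥ 3) + 0.5 × P(difference within 2).

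- 15% vs 35%: 0.8138 + 0.5 × 0.1805 = 0.904. The plan says "This study design has 90% power to identify the correct regimen as most promising".
- 40% vs 60%: 0.7787 + 0.5 × 0.2058 = 0.882. The plan says "we will still have sufficient power (>88%) to determine that one arm is more promising".
- 10% vs 30%: 0.8344 + 0.5 × 0.1630 = 0.916. The plan says more than 90%.

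At 15% vs 35%, a threshold of 2 would give 0.938 and a threshold of 4 would give 0.856, so 3 is the threshold behind the stated 90%.

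**Step 3: equal true rates, Arm B reads inflated.** Inflation is modelled as a higher apparent rate in Arm B: 1/26 = 3.8 points for an average of one extra responder, 2/26 = 7.7 points for two. At a true rate of 25% in both arms:

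| Extra Arm B responders | Apparent rate, A / B | B leads by ≥ 3 | Within 2 | A leads by ≥ 3 |
|---|---|---|---|---|
| 0 | 25.0% / 25.0% | 21.1% | 57.8% | 21.1% |
| 1 | 25.0% / 28.8% | 31.9% | 54.5% | 13.6% |
| 2 | 25.0% / 32.7% | 44.0% | 47.7% | 8.3% |

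The chance that B leads by at least 3 depends little on the assumed true rate. It goes from 16.3% to 28.7% to 42.8% at a true rate of 15%, and from 23.4% to 33.4% to 44.5% at 35%.

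**Step 4: Arm A truly better (35% vs 15%), Arm B reads inflated.**

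- No inflation: 0.8138 + 0.5 × 0.1805 = 90.4% correct selection.
- One extra Arm B responder (apparent 18.8%): 0.7069 + 0.5 × 0.2765 = 84.5%.
- Two extra (apparent 22.7%): 0.5870 + 0.5 × 0.3739 = 77.4%.

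**Step 5: Arm B truly better (35% vs 15%), Arm B reads inflated by one.** 0.8854 + 0.5 × 0.1121 = 94.1%, above the unbiased 90.4%. Bias in the expected direction leads to a wrong choice only when the arms are similar or Arm A is better.

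**The case against.** Local reading is an explicit choice in a 52-patient screening study that feeds a Phase III trial. No sections conflict and no stated figure is wrong. That stands: this is a proposed improvement to the design, not the correction of an error.

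A reader might infer that the radiologists are unmasked, or that the trial is declared open-label. The documents say neither. Section 4.2 sends the arm to the site, and nothing says it reaches the radiologist. What can be said is that masking is not specified where the site knows the arm.

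A reader might also infer that the only check is optional and that missed responses are never looked for. Section 12.1.2 makes the request for source reports mandatory and does not limit verification to claimed responders. What remains is that those reports carry the same site read, image requests are optional, and no selection rule is given. The review panel or Principal Investigator in 11.1.4.2 confirms only progression based on non-target lesions alone.

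Some protection already exists. Required imaging and eligibility documents are submitted before randomization (4.2), the same technique is required at baseline and follow-up (11.1.3), and both arms are scanned every 8 weeks. Expectation can therefore act mainly on follow-up measurements.

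Section 13.1.2 argues that 20-29% shrinkage is real and not measurement noise. The documents do not show that this range is especially open to judgement. But that argument concerns random variation, not expectation tied to arm, and section 11.1.3 itself accepts that extra information (PET) may bias an investigator.

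Finally, removing the arm from every imaging request could deprive safety reads of drug-exposure information. CT is recommended for grade 2 or higher respiratory symptoms (Table 2, 6.2.3), and pneumonitis is listed for trametinib (7.2). This is a sound objection, and the fix is confined to trial measurements because of it.

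**Conclusion.** The point holds as a gap in specification. The primary endpoint is read at a site that knows the arm, no masking is specified, and the choice of regimen can turn on 3 of 26 patients. If reading added an average of one Arm B responder, a lead for B between equal arms would become about half as likely again (31.9 / 21.1 = 1.5). Correct selection of a truly better Arm A would fall by 90.4 − 84.5 = 5.9 points.

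These figures assume the size and direction of the bias, and the equal 25% rates are not the plan's own scenario. They show how sensitive the rule is; they are not evidence that bias would occur. Nor does the choice follow the raw difference alone: leads of 2 or fewer go to other factors, and toxicity can override a larger lead. Toxicity does not, however, correct a biased response count. Masking would address bias related to arm, not random reading error or differences between sites.

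**What to change.** In section 11.1.7, state that the site radiologist records target-lesion measurements for the trial without being told the treatment arm. The arm is left off the tumour measurement form and the measurement request. Clinical and safety reads may still receive drug-exposure information.

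In section 12.1.2, state that any image verification is requested either for all patients or for the same fraction in each arm, whatever response was reported.

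The cost is a sentence in each section and a change to the forms. Sample size, endpoint, scan schedule and decision rule do not change. No additional reader should be needed, though that is a practical judgement on which the documents are silent. Masking will be imperfect, because the arm may be inferred from clinical notes, prior reports or crossover. Keeping the arm out of the measurement step while leaving it available for safety reads takes some coordination at each site.
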